**Research Coordinator**

[name]  
[name]  
[name]

**Population:** Patients discharged home from Memorial Hermann Hospital

**Number of Sites:** One – UT Houston

**Study Duration:** 30 months

**Subject Duration:** 6 months

**Background and Significance**

Improvements in stroke prevention, acute treatment, and organized systems of care for acute stroke are all contributing to declines in stroke mortality observed over the past decade. However, with increasing survival after stroke and expected increases in stroke incidence related to population aging, the prevalence of stroke is projected to increase by 3.4 million in 2030. Despite these projections, there has been little research on post-acute care models for stroke survivors.

IRB NUMBER: HSC-MS-18-0925

IRB APPROVAL DATE: 11/10/2020

Stroke incidence, mortality, and recurrence vary by race. African Americans, Hispanic Americans, and American Natives have higher risk of stroke than Caucasian Americans. Projected increases in stroke prevalence also vary by racial and ethnic category, with the largest rises expected in men and women of Hispanic ethnicity and African American race. Systems of care for stroke survivors must be developed with mechanisms to identify and address racial disparities in stroke outcomes.

Hypertension is the most important risk factor for ischemic stroke and hemorrhagic stroke. Small reductions in systolic BP after stroke (5 mmHg) are associated with greater than 20% reduction in recurrent stroke risk. However, available data suggests that hypertension remains poorly controlled after the incident stroke. A report from the Reasons for Geographic and Racial Differences in Stroke (**REGARDS**) observational study revealed that risk factor awareness and control were poor in participants who self-reported a history of stroke. Only 66.7% of stroke survivors had controlled BP, and African American stroke survivors were more likely to have undiagnosed hypertension and uncontrolled hypertension (among those treated) than White stroke survivors. Baseline visit data from the Secondary Prevention of Small Subcortical Strokes (**SPS3**) trial support REGARDS data. Among US participants, 44% of ischemic stroke survivors had controlled BP three months after stroke and African Americans were more likely to have uncontrolled BP. Investigators from The Differences in the Imaging of Primary Hemorrhage based on Ethnicity or Race (**DECIPHER**) project reported poor BP control 30 days and 1 year after hemorrhagic stroke. In this study, BP was controlled (less than 140/90) for 47.2% of participants at 30 days and for 41.7% one year after stroke, and BP control was poor in African Americans.

Factors associated with BP control in African Americans have been studied extensively. These include social and economic factors, condition and therapy-related factors, health care system and clinician factors, patient-related factors, and patient-physician relationship factors. Uncontrolled BP may be specifically related to medication cost, access to healthcare, access to providers, medication complexity, patient beliefs and perceptions, patient educational achievement and socioeconomic status, patient response to and side effects of medications, sodium intake, patient depression and demoralization, perceived racism and discrimination, social networks and support, physician prescribing practices, physician communication and empathy, neighborhood segregation, and others.

There are fewer studies of uncontrolled BP in stroke survivors overall, but among published studies, race, socioeconomic status, medication adherence, self-efficacy, marital status, and level of independence have been associated with BP control. Access to care, medication adherence, and medication prescribing patterns do not fully explain disparities in BP control in stroke survivors. Among 2972 insured stroke survivors followed in the Kaiser Quality Improvement in Stroke Prevention (**QUISP**) study, odds of BP control in African Americans was 41% less than that observed in White Americans despite similar rates of medication adherence and attendance at outpatient visits and higher median number of medications. Disparities in control may be explained by physiologic factors such as duration of hypertension, differential response to medications according to race, and medical comorbidities such as sleep apnea and chronic kidney disease. The presence and differential impact of post-stroke depression, cognitive impairment, social isolation, and caregiver burden may add to the complexity of BP control in hypertensive stroke survivors.

The most effective interventions for BP control in the general population of African Americans target more than one barrier to control. Successful interventions include those that incorporate a team-based approach to care, that utilize a pharmacist or health professional other than the primary care provider, and those that utilize telehealth and home BP monitoring. Among stroke patients, isolated behavioral and educational interventions have not been shown to impact BP control. Organizational interventions, such as those incorporating collaborations among multidisciplinary teams, integrated care services, revision of pharmacists' roles, and/or knowledge and quality management protocols show evidence supporting mild improvements in BP control. To our knowledge, no studies have shown benefit for reducing disparities in BP control among stroke survivors.

We will implement a pilot trial of a telehealth intervention for BP control at the Memorial Hermann Hospital-TMC campus focusing on patients at highest risk for uncontrolled blood pressure. The intervention will address general and stroke-related factors associated with racial disparities in BP control. We will assess feasibility of implementation of the trial and will use the measures and outcomes assessed in the pilot to examine knowledge gaps.

## Specific Aims

### Aim 1 will focus on the identification of hospitalized ischemic and hemorrhagic stroke patients at risk for uncontrolled BP after hospital discharge.

- We will develop a checklist to be completed by the discharge nurse navigator or social worker for early identification of stroke inpatients at risk for uncontrolled BP. The checklist will include existing information from the patient medical record (race and insurance) and clinical information including stroke type and etiology in order to document the presence of known risk factors for uncontrolled BP. Key known risk factors include uninsured status, Medicaid payer status, hypertensive intracerebral hemorrhage, small vessel ischemic stroke, and patients on  $\geq 2$  hypertensive medications. The checklist will be used to determine which patients should be screened for study eligibility.

### Aim 2 will shift from the planning portion of the study to the pilot trial, which will simulate a larger trial and allow evaluation of intervention components and outcome measures and estimation of effect sizes and attrition rates.

- Aim 2a: To examine the suitability of key study components and outcome measures intended for a future larger trial, we will randomize 50 patients to the intervention and 50 patients to usual care. We will determine the proportion of randomized patients who complete the intervention visits, the proportion of patients (by group) who complete the outcome assessments, and barriers to intervention and 6-month outcome assessment completion.
- Aim 2b: To examine the suitability and ease of use of the telehealth tool and effectiveness of components of the intervention, we will develop a CRF to capture patient feedback to be integrated into the design of the future, larger trial.
- Aim 2c: To estimate key parameters needed to adequately power a larger randomized trial, we will calculate the effect of the intervention on the ambulatory systolic blood pressure at 6 months relative to usual care; the probability using Bayesian methods that this effect size exists; the enrollment rate; and the attrition rate.

## Study Procedures:

## Eligibility Criteria

Ischemic and hemorrhagic stroke patients (N=100) identified as potentially eligible by the checklist (at least one of the following high risk criteria: uninsured, Medicaid payer status, small vessel ischemic stroke, hypertensive ICH, planning on discharging on  $\geq 2$  hypertension medications) will be eligible if they also meet the following inclusion criteria: age  $\geq 18$ ; presence of hypertension (by clinical history or hospital BP  $\geq 130/80$  mmHg on two occasions); plan to discharge home after stroke; ability to provide consent (patient or caregiver); ability to communicate in English. Exclusion criteria will include modified Rankin scale  $> 4$  at the time of enrollment (severe disability), life expectancy  $< 1$  year or terminal illness, eGFR  $< 30$  at time of discharge, pregnancy, symptomatic flow limiting carotid stenosis without plan for intervention; urine toxicology positive for cocaine or methamphetamine or history of use; long-term BP goal  $\geq 130/80$  mmHg according to clinical team; and inability to comply with study procedures \* (severe expressive language impairment, deafness, blindness, or other physical; cognitive; or social issues limiting ability to adhere to procedures).

## Screening and Randomization

Sequential eligible patients will be approached prior to discharge to assess their interest in participating in the trial. Informed consent will be obtained from patients. Caregivers will provide consent for patients with aphasia who are otherwise eligible. Baseline assessments of socioeconomic status (education and income), medication adherence, medication adherence self-efficacy, cognition, and social support will be completed prior to randomization. We will use an internet-based system to randomize patients (1:1) to intervention versus usual care using a block design with permuted blocks of 2 to 4. The randomization allocation sequence will be developed by a statistician not involved in enrollment procedures. We will stratify based on insurance status (insured vs uninsured) and race (African American vs other) to assure that groups are balanced with respect to baseline risk. Consort criteria for the design of parallel group randomized trials will be followed.

## Intervention

Components of the telehealth intervention will target behaviors associated with racial disparities (African American focused) in BP control. At the time of discharge, intervention patients will receive a package containing an iPad (with a data plan) and a blue tooth enabled blood pressure monitor that allows automatic transmission of encrypted BP data to the study team (QardioARM). Patients will be allowed to use their own smart device if it is compatible with the BP device). Patients and/or caregivers will be instructed in use of equipment and the first video telehealth visit will be arranged. They will complete questionnaires including a depression screen, a dietary assessment, a cognitive screen, and a sleep apnea screen prior to discharge. Patients will receive a phone call at 72 hours by the discharge nurse navigator or social worker (standard of care) to assure that they have received their medications and follow-up appointments. The first telehealth visit will occur 7 days after discharge. A stroke prevention-trained nurse practitioner (**NP**) or **MD**, social worker (**SW**), and pharmacist will attend this video telehealth visit. The NP will review the participant's hospital records and depression, dietary, and sleep apnea screens, will reinforce the care plan based on patient-specific needs. The NP or MD will counsel patients on salt reduction, the Mediterranean diet, and the importance of diet and exercise for stroke prevention. The NP (or MD) and pharmacist will review the BP data to determine the need for medication adjustment. The pharmacist will discuss side effects and

interactions. Treatment of hypertension and selection of BP lowering medications will be in accordance with latest published guidelines for BP management. The SW will assess the need for medication assistance and other resources. The care plan will be shared with primary care providers (PCP) and patients will be referred to a PCP if they do not have one. The SW will assist uninsured patients in applying for Texas County Indigent Care programs.

Participants will be prompted to transmit BP logs through the telemonitoring device every 2 weeks until average BP is < 130/80, then monthly thereafter. Uncontrolled BP will prompt a call from the pharmacist to discuss medication adherence and the need for further titration. Subsequent video telehealth visits for intervention patients will be attended by the NP (or MD) and pharmacist 1 month, 3 months, and 5 months after enrollment. Care plans will be reviewed and medication and lifestyle adherence will be assessed. Medications will be adjusted as appropriate. Participants will complete electronic health care utilization and recurrent vascular CRFs using the iPad at 3 months and 6 months (final outcome). Participants will receive educational messaging once every other week throughout the study period. Messages will be sent to the participants' cellular phones. The messages will contain one of the following: a reminder to monitor BP, information from about lifestyle and diet for BP reduction, or a message from the pharmacist about medication adherence. Final outcome assessments (detailed below) will occur at 6 months.

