#### **Usual Care (Control) Group**

Participants randomized to usual care will complete questionnaires including a depression screen, a dietary assessment, a cognitive screen, and a sleep apnea screen prior to discharge. A summary of the assessments will be given to the patient and they will be instructed to follow-up with their PCP and to monitor their BP. They will be contacted by the discharge nurse navigator or social worker at 72 hours to as per usual care to determine if they have received their medication and made their appointments. They will be offered a standard of care hospital follow up appointment with a stroke neurologist or nurse practitioner at the clinic. The RC will contact participants at 30-days, 90-days, 150-days to encourage continued participation. The RC will complete a telephone CRFs to obtain information about readmissions, hospital visits, and recurrent vascular events at 30 days and 90 days. Final outcome assessments (detailed below) will occur at 6 months.

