## **Primary Clinical Outcomes**

The primary clinical outcome will be the daytime ambulatory systolic blood pressure at 6 months. Secondary clinical outcomes will include the following: daytime ambulatory diastolic blood pressure, nighttime ambulatory systolic and diastolic blood pressure; BMI at 6 months; recurrent vascular event rate (stroke, myocardial infarction, acute cardiac death); and acute healthcare utilization rate (hospital readmission and acute care visits to emergency room and/or urgent care). The 6- month behavioral outcomes will include change in self-efficacy for taking medication as prescribed, medication adherence, and caregiver burden. Patient satisfaction will be assessed using scores obtained from the Patient Telemedicine Satisfaction Survey.

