## **Outcome Assessments**

All enrolled patients will have final 6-month outcomes either in-clinic or by home visit with the research coordinator. Final BP will be assessed using a validated ambulatory blood pressure monitor (ABPM). The patient will be fitted with the ABPM at the final visit and will receive a Fedex envelope in which to return the ABPM after 24 hours. Weight and height will be assessed for BMI. Final healthcare utilization and recurrent vascular event CRFs will be completed and behavioral outcomes will be assessed using MASES, MMAS, and the Zarit Caregiver Burden Questionnaire. Satisfaction with telehealth visits will be assessed using the Telemedicine Satisfaction Survey (intervention arm). Patients will be compensated for final study visits (\$50).

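### Vascular events and acute healthcare use are collected by different methods in the two arms, and no rule says which forms count in the comparison

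*Combined protocol and SAP*

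**What the plan says.** The combined protocol and SAP names two event-type secondary outcomes under Primary Clinical Outcomes. One concerns care use: "acute healthcare utilization rate (hospital readmission and acute care visits to emergency room and/or urgent care"). The other concerns vascular events: "recurrent vascular event rate (stroke, myocardial infarction, acute cardiac death"). The statistical section lists both for secondary analysis.

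Collection depends on the arm:

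- **Intervention** (Intervention section): "Participants will complete electronic health care utilization and recurrent vascular CRFs using the iPad at 3 months and 6 months (final outcome"). The device comes with the intervention package: "intervention patients will receive a package containing an iPad (with a data plan"). Patients may use their own compatible device instead.
- **Usual care** (Usual Care section): "The RC will complete a telephone CRFs to obtain information about readmissions, hospital visits, and recurrent vascular events at 30 days and 90 days".
- **Both arms at 6 months** (Outcome Assessments): "All enrolled patients will have final 6-month outcomes either in-clinic or by home visit with the research coordinator". Final utilization and vascular event forms are completed then, but the section does not say on what medium or by whom.

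No section gives the recall period of any form, says whether interim forms are combined with the 6-month form, or describes confirmation of events from records or by adjudication.

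Aim 2a sets the purpose: "To examine the suitability of key study components and outcome measures intended for a future larger trial". It also asks for "the proportion of patients (by group) who complete the outcome assessments".

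**The concern.** Before 6 months the arms differ in who fills in the event form (patient or coordinator), in mode (electronic or telephone) and in number of forms (one or two). At 6 months the mode may differ as well, since the Intervention section puts the form on the iPad. When the method of finding events is tied to the arm, part of any difference in event rates can come from the method rather than from the treatment.

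The direction cannot be predicted. Self-completion and one fewer form could lower the intervention count. Clinician video visits at 7 days and at 1, 3 and 5 months could raise it, although no event form is tied to them. Content may differ too: the usual-care telephone form is described in terms of readmissions, hospital visits and vascular events, while the outcome definition includes urgent care.

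What is at stake is less the pilot's own result than Aim 2a. A scheme in which method and arm coincide cannot show whether these two measures work alike in both groups, and it could be carried into the larger trial. Acute cardiac death cannot be self-reported, so among the vascular components the concern covers only the non-fatal ones.

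**Working it through.** The plan gives no event rate, capture rate or power figure for these outcomes, so there is no figure of its own to reproduce. The schedule can be counted from the text; the size can only be illustrated.

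**Step 1. Count the forms.**

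| | Intervention | Usual care |
|---|---|---|
| Before 6 months | 1 (3 months, iPad, patient) | 2 (30 and 90 days, telephone, coordinator) |
| At 6 months | 1 (iPad or coordinator visit: unclear) | 1 (coordinator visit) |
| Total | 2 | 3 |

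If each form covered the time since the previous one (an assumption), recall windows would be about 90 + 90 days against 30 + 60 + 90 days.

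**Step 2. Illustrate the size for acute-care use. Every rate below is assumed.**

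Observed rate = T × [s × (c + r × (1 − c)) + (1 − s) × c_max], where

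- T = 0.30, the true 6-month proportion with acute-care use, equal in both arms;
- s = 0.5 or 0.7, the share of events in months 0 to 3;
- c = the arm's interim capture: 85% vs 95%, 75% vs 90% or 60% vs 90% (intervention vs usual care);
- c_max = the higher capture of the pair, used in both arms after month 3;
- r = the share of missed early events that the 6-month form recovers.

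Worked case, s = 0.7, 60% vs 90%, r = 0:

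- intervention 0.30 × (0.7 × 0.60 + 0.3 × 0.90) = 20.70%;
- usual care 0.30 × (0.7 × 0.90 + 0.3 × 0.90) = 27.00%;
- RR = 20.70/27.00 = 0.77; difference 6.30 points.

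| r | RR, s = 0.5 | RR, s = 0.7 | Largest RR if reversed | Difference, points |
|---|---|---|---|---|
| 0 | 0.95, 0.92, 0.83 | 0.93, 0.88, 0.77 | 1.30 | 1.5 to 6.3 |
| 0.5 | 0.97, 0.96, 0.92 | 0.96, 0.94, 0.89 | 1.13 | 0.8 to 3.2 |
| 0.8 | 0.99, 0.98, 0.97 | 0.99, 0.98, 0.96 | 1.05 | 0.3 to 1.3 |
| 1 | 1.00 | 1.00 | 1.00 | 0 |

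**Step 3. Why this table is not an outer bound.** It gives both arms equal capture after month 3. If the 6-month mode also differs and capture is 60% vs 90% throughout with nothing recovered, RR = 0.60/0.90 = 0.67 (1.50 reversed) and the difference is 0.30 × (0.90 − 0.60) = 9.0 points.

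**Step 4. Compare with sampling error at 50 per arm.** Half-width = 1.96 × √[p1(1 − p1)/50 + p2(1 − p2)/50].

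- Cases in the table with r from 0 to 0.8: 16.7 to 17.8 points.
- Step 3 case (18% vs 27%): 1.96 × √(0.1476/50 + 0.1971/50) = 16.3 points.

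**Step 5. Size at which the artefact equals the half-width.** n per arm = 1.96² × [p1(1 − p1) + p2(1 − p2)]/d².

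- d = 6.30 points (r = 0): about 350.
- d = 3.15 points (r = 0.5): about 1,505.
- d = 9.0 points (Step 3): 3.8416 × 0.3447/0.0081, about 163.

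The larger trial's size is not given.

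**Step 6. Non-fatal vascular events.** T cancels from the RR, so the ratios are the same. With T assumed at 5% to 10%, the artefact is 0.13 to 1.05 events per 50 patients at r = 0 and 0.06 to 0.52 at r = 0.5. In the Step 3 case with T = 10% it is 50 × 0.10 × 0.30 = 1.5 events.

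The formula treats each outcome as a proportion of patients while s is a share of events, which is a further simplification.

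**The case against.** The best defence is that the comparison rests on a common 6-month assessment. The Intervention section marks only the 6-month form as the final outcome, both arm descriptions place final outcome assessment at 6 months, and Outcome Assessments puts every patient in front of the coordinator then. Nothing says interim forms are pooled, and a recall period would normally be printed on the form itself, which is not among the documents. If that form covers the whole period and alone supplies the comparison, the interim difference drops out (r = 1, RR = 1.00). This stands as a plausible reading. It does not settle the matter: the plan states neither condition, and the Intervention section puts even that arm's 6-month form on the iPad.

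The defence is also right that these are secondary outcomes of a feasibility-sized pilot, and that counting only forms common to both arms would lose deaths and any event learned before a patient dropped out. The fix below allows for that.

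A reader might infer three stronger things that the documents do not support:

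- *That the comparison is biased, or biased in favour of the intervention.* Neither the pooling nor the direction is stated.
- *That the Intervention and Outcome Assessments sections contradict each other.* An iPad form could be completed at the coordinator visit; the mode is unclear rather than contradictory.
- *That the statistical section's list of completion time points neglects usual-care interim forms.* Its intervention-only entries at 7 days and 1, 3 and 5 months match the four video visits, so its 3-month entry most naturally means the visit, and its 6-month entry covers all patients.

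**Conclusion.** The concern holds in conditional form, at minor severity. The unequal scheme is stated in the text and is not merely missing detail. Harm follows only if interim forms feed the comparison or the 6-month mode differs by arm, and the plan leaves both open.

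Under the assumed rates the artefact in acute-care use is 0.3 to 6.3 points, or 9.0 if unequal capture persists to 6 months. Each is below the half-width of 16 to 18 points at 50 per arm. These figures show scale only; neither size nor direction can be derived from the documents. Daytime ambulatory systolic pressure and the Aim 2c quantities (effect on systolic pressure and its probability, enrollment, attrition) are not touched. The reason to act is Aim 2a: the measures are being tried out for a larger trial, where sampling error would no longer hide such an artefact.

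**What to change.** - At 6 months use one identical coordinator-administered utilization and vascular event form in both arms. It should cover the whole period since discharge and every self-reportable component of the two outcomes, with urgent care named. Make it the main source for the comparison of non-fatal events.
- State that mode in both the Intervention and Outcome Assessments sections.
- If an interim form is to enter the comparison, give it the same content, mode and timing (90 days) in both arms.
- Count deaths, including acute cardiac death, from any source in both arms.
- Report separately the events known only from the 30-day form, from video visits, or from patients without a 6-month form, and add a sensitivity analysis that includes them.
- The iPad form may stay for telehealth feasibility, but not as a source for the comparison.

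**Cost.** The 6-month option needs wording changes and no extra calls, but relies on recall over 6 months. Equalising the 90-day form adds 50 × 1 = 50 short calls by the coordinator who already calls controls. Keeping iPad forms alongside adds to the form burden, which Risks and Benefits undertakes to minimise. Either way, non-fatal events remain self-reported to a coordinator for whom no masking is described.
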